2.1 Primary Objective

- To estimate the clinical activity of tyrosine kinase inhibitors matched to the tumor-specific fusion kinase in patients with metastatic melanoma.

2.2 Secondary Objectives

- To estimate tumor stability in melanoma patients treated with kinase inhibitors matched to the tumor-specific fusion kinase.
- To estimate survival in melanoma patients treated with kinase inhibitors matched to the tumor-specific fusion kinase.
- To examine the safety and tolerability of kinase inhibitors in patients with melanoma with a fusion kinase.

2.3 Exploratory Objectives, Other Assessments

- To explore molecular mechanisms of resistance for patients who progress on therapy.

3 Endpoints of the Study

3.1 Primary Endpoint

- Overall response rate (ORR) by Response Evaluation Criteria in Solid Tumors (RECIST) v1.1 at 24 weeks.

3.2 Secondary Endpoints

- Clinical benefit rate (CBR) (with clinical benefit defined as complete response (CR) or partial response (PR) or stable disease (SD) for >24 weeks).
- Determination of progression-free survival (PFS) and overall survival (OS).
- Evaluation of the adverse effect profile of each kinase inhibitor, using National Cancer Institute Common Terminology Criteria for Adverse Events (NCI CTCAE) v4.03.

3.3 Exploratory Endpoints

- Exploratory endpoints to include assessment of expression levels of the fusion kinase protein, before and during treatment, reported as percentage by immunohistochemistry (IHC) staining.

4 Study Design

4.1 Characteristics

This is a phase II prospective multi-center basket trial designed to test the hypothesis that targeting specific kinase fusions in metastatic melanoma with kinase inhibitors matched to the activated kinase fusion will result in tumor response. The study design is a 2-stage optimal design. Patients with a eligible kinase fusion in their melanoma, as identified by a CLIA-approved laboratory (targeted next-generation sequencing of tumor tissue, fluorescence in situ hybridization and immunohistochemistry) will be offered enrollment in this protocol and will be treated in one of five baskets. As testing for fusion kinases is not currently part of the standard of care for melanoma, a separate protocol will provide screening for kinase fusions for patients with BRAF wild-type melanoma in a CLIA-approved laboratory at UCSF. Based on the kinase fusions identified, patients will be stratified as follows:

Table 1. Kinase Fusion and Assigned Drug

MET fusion	Capmatinib 400 mg PO BID
ALK fusion	Ceritinib 450 mg PO q day (with low-fat meal)
RET fusion	Regorafenib 160 mg PO q day (first 21 days of each 28 day cycle)
BRAF fusion	Regorafenib 160 mg PO q day (first 21 days of each 28 day cycle)
NTRK1 fusion NTRK2 fusion NTRK 3 fusion	Entrectinib 600 mg PO q day
ROS1 fusion	Entrectinib 600 mg PO q day

The dose of capmatinib at 400 mg PO BID is based on the recommended phase II dose (RP2D) by Novartis. Ceritinib at 450 mg PO daily with a low-fat meal (approximately 100-500 calories, 1.5-15 grams of fat) demonstrated comparable AUC_{0-24h} and C_{max} at Cycle 2 Day 1 to patients treated with ceritinib 750 mg under fasting conditions (the FDA-approved dose for ALK-rearranged NSCLC resistant to intolerant to crizotinib). Both ceritinib dosing regimens showed similar rates of AEs but GI related AEs and dose interruptions were fewer with dosing at 450mg PO daily with a low-fat meal, and for this reason is the chosen dosing. For regorafenib we will dose at 160 mg PO daily (first 21 days of each 28 day cycle) which is the FDA-approved dose for both colon cancer and GIST. The dose of entrectinib at 600 mg PO QD is the RP2D based on two Phase 1 studies conducted by Ignyta. Please refer to Table 1 for drug assignments and Table 2 for drug dose regimens.

4.2 Number of Subjects

We anticipate enrollment of 35 evaluable patients to this study. Identification of a fusion kinase is required for eligibility and testing for fusion kinases is not standard of care. A separate UCSF research protocol will screen melanoma patients in need of treatment who are wild-type for BRAF mutation for fusion kinases (PI: [name]).

The sample size is based on a 2-stage Simon's optimal design using ORR at 24 weeks as primary efficacy endpoint. We assume that a response rate of 10% would be unacceptable and a response rate of 30% would be considered clinically meaningful. Under type I error of 0.05 and type II error of 0.15, in the first stage of this design, 11 patients will be accrued. If 1 or fewer patients achieve a response among the initial 11 patients, the trial will be terminated. If at least 2 patients achieve a response among these 11 patients, then an additional 24 patients will be accrued to the second stage. If 6 or fewer patients achieve a response, then the trial will be terminated. Under these conditions, if the response rate is 0.1, the probability of ending the trial during stage 1 is 0.70. If the true response rate is 0.3, the probability that the trial will be stopped in stage I is 0.11.

If 35 evaluable patients with follow-up of at least 12 months are enrolled, but fewer than 5 patients are assigned to a given drug, the study will continue to enroll patients until we have enrolled at least 5 patients for each of the 4 study drugs with a max of 50 patients enrolled.

We anticipate enrollment of 35 evaluable patients to this study. Evaluable patients would be those with baseline staging, treatment for at least 8 weeks, and at least one post-baseline staging scan while on treatment. We estimate a drop-out rate of 20%, and therefore 44 patients will be enrolled and started on treatment. Kinase fusion melanoma prevalence is currently estimated at 10% of BRAF/NRAS WT melanomas, thus we anticipate screening 440 patients to enroll 44 patients.

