Secondary Objectives	
 To estimate tumor stability in kinase fusion melanoma patients treated with kinase inhibitors matched to the activated fusion partner. To estimate survival in kinase fusion melanoma patients treated with kinase inhibitors matched to the activated fusion partner. To examine the safety and tolerability of kinase inhibitors in patients with the kinase fusion targets.
Exploratory Objectives	
 To explore molecular mechanisms of resistance for patients who progress on therapy.
Primary Endpoint	
 Confirmed ORR by RECIST v1.1 at 24 weeks.
Secondary Endpoints	
 Confirmed CBR (defined as CR or PR or SD for >24 weeks). Determination of PFS and OS. Evaluation of the adverse effect profile, using CTCAE v4.03, of each kinase inhibitor.
Exploratory Endpoints	
 Exploratory endpoints to include assessment of expression levels of the fusion kinase protein, reported as percentage by IHC staining. Measures taken at baseline and after 4 weeks of therapy will be summarized. Changes in expression level will be assessed between baskets using a paired t-test if data permit. For patients who progress on therapy, an additional biopsy may be obtained and will be compared with baseline expression levels if data permit.
Study Design	This is a phase II multi-center prospective basket trial designed to test the hypothesis that targeting specific kinase fusions in metastatic melanoma with pre-specified kinase inhibitors will result in objective tumor shrinkage and durable response. The study design is a 2 stage optimal design with a sample size of N=35, with n1=11 during stage I and n2=24 during stage II. If 1 or fewer responses are observed during stage I, the trial will be stopped. If 6 or fewer responses are observed by the end of stage II, the trial will be stopped.

Number of patients	Estimating a drop-out rate of 20%, we anticipate enrolling 44 patients to accrue 35 evaluable patients.
Study Drugs	Capmatinib, Entrectinib, Ceritinib, Regorafenib
Safety Assessments	Physical exam with evaluation of vital signs, performance status, and toxicity grading as per CTCAE v4.03. Clinical laboratory evaluations including CBC, CMP.
Efficacy Assessments	ORR and CBR to be assessed as per RECIST v1.1 criteria.

List of Abbreviations

AE	adverse event
ALT	alanine aminotransferase
AST	aspartate aminotransferase

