- all SAEs that occur after informed consent and through 30 days after the decision to discontinue study treatment (or the date the subject is deemed to be a screen failure);
- any SAEs assessed as related to study treatment or study procedures, even if the SAE occurs more than 30 days after the decision to discontinue study treatment;
- although most hospitalizations necessitate reporting of an SAE, some hospitalizations do not require SAE reporting, as follows:
 - elective or previously scheduled surgeries or procedures for pre-existing conditions that have not worsened after initiation of treatment (e.g., a previously scheduled ventral hernia repair);
 - pre-specified study hospitalizations for observation; or
 - events that result in hospital stays of fewer than 24 hours and that do not require admission (e.g., an emergency room visit for hematuria that results in a diagnosis of cystitis and discharge to home on oral antibiotics). SAEs must, however, be reported for any surgical or procedural complication resulting in prolongation of the hospitalization.

9 Statistical Considerations and Evaluation of Results

This is a phase II, prospective, multicenter, single arm trial to test the hypothesis that targeting specific kinase fusions in melanoma with pre-specified kinase inhibitors will result in objective tumor response. Patients will be screened for one of the eligible fusion proteins under a separate protocol, and if identified will be treated in this study in one of six baskets (ALK, NTRK, ROS1, RET, MET, or BRAF kinase fusions). The primary endpoint is composite (all fusion types analyzed together) confirmed objective response as defined as a complete or partial response as per RECIST v1.1 criteria. Standard therapies such as IL-2 and ipilimumab have shown response rates of approximately 10%. The newly approved immunotherapy pembrolizumab has a response rate of approximately 30%.

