A 2-stage optimal design will be employed in which a 10% response rate is considered not promising, a 30% response rate is considered promising, and the probabilities of a type I error (falsely accepting a non-promising therapy) and type II error (falsely rejecting a promising therapy) are set at 0.05 and 0.1, respectively. In this scenario, the maximum trial size would be 35 evaluable patients. Evaluable patients would be those with baseline staging, treatment for at least one cycle (with at least 90% of intended doses administered during cycle 1), and at least one post-baseline staging scan while on treatment. We estimate a drop-out rate of 20%, and therefore 44 patients will be enrolled and started on treatment. In the first stage of this design, 11 patients will be accrued. If 1 or fewer patients achieve a response among the initial 11 patients, the trial will be terminated. If at least 2 patients achieve a response among these 11 patients, then an additional 24 patients will be accrued to the second stage. If 6 or fewer patients achieve a response in the second stage, the trial will be terminated. Under these conditions, if the response rate is 0.1, the probability of ending the trial during stage 1 is 0.70. If the true response rate is 0.3, the probability that the trial will be stopped in stage I is 0.11.

Analysis of study results will be carried out by the study statistician and will include overall response rate (ORR) estimations of ALK, NTRK, ROS1, RET, MET, and BRAF rearrangement-positive patients.

Clinical benefit rate (CBR) defined as the proportion of patients achieving a complete response (CR) or partial response (PR) or stable disease (SD) for > 24 weeks will be estimated for each arm along with a 95% confidence interval.

Progression free survival (PFS) defined as the time from treatment start to the progression or death and overall survival defined as the time from treatment start to death will be estimated using Kaplan-Meier methodology.

Frequencies of toxicities will be tabulated according to CTCAE v4.03 to assess drug safety and tolerability.

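### Section 4.2 both terminates the trial at 6 or fewer responses and continues enrolment to 50 if a drug has fewer than 5 patients; the plan neither reconciles the two rules nor says whether added patients enter the pooled test

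*Combined protocol and SAP*

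**What the plan says.** Section 4.2 (Number of Subjects) sets a Simon two-stage design: 11 patients, then 24 more if at least 2 of the 11 respond. The final rule is "If 6 or fewer patients achieve a response, then the trial will be terminated". The abstract has the same rule: "If 6 or fewer responses are observed by the end of stage II, the trial will be stopped".

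The next paragraph of Section 4.2 adds a second rule. Its trigger is "If 35 evaluable patients with follow-up of at least 12 months are enrolled, but fewer than 5 patients are assigned to a given drug". Enrolment then goes on "until we have enrolled at least 5 patients for each of the 4 study drugs with a max of 50 patients enrolled". This paragraph does not mention the number of responses and does not refer back to the termination rule.

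The rest of the document is written for 35 evaluable patients. The abstract has "Estimating a drop-out rate of 20%, we anticipate enrolling 44 patients to accrue 35 evaluable patients". Section 9 (Statistical Considerations) has "In this scenario, the maximum trial size would be 35 evaluable patients". Neither mentions the five-per-drug rule or the cap of 50. Section 9 defines the primary analysis as pooled, "The primary endpoint is composite (all fusion types analyzed together) confirmed objective response", and also plans "overall response rate (ORR) estimations of ALK, NTRK, ROS1, RET, MET, and BRAF rearrangement-positive patients". No section says which of these analyses the patients beyond 35 would enter.

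**The concern.** Suppose the trial passes stage 1, reaches 35 evaluable patients with 6 or fewer responses, and one drug has fewer than 5 patients. One paragraph then closes the trial and the next keeps it open. Nothing ranks them.

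The extension trigger refers to at least 12 months of follow-up, while the primary endpoint is response at 24 weeks. Whoever has to choose between the rules would therefore already know the response count. If the trial went on, the added patients went into the pooled test and the cut-off stayed at 6, a trial that had failed at 35 could become a success at 37 or 40. The stated type I error of 0.05 would then no longer hold.

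**Working it through.** **Inputs.** From Section 4.2: null rate 10%, target rate 30%, type I error 0.05, type II error 0.15; stop at 1 or fewer of 11; terminate at 6 or fewer of 35; 20% drop-out; cap of 50 enrolled. From Section 1.1: fusion frequencies ROS1 17, NTRK1 16, ALK 10, BRAF 5, RET 3 (percent); MET is named without a figure.

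**1. The plan's own figures.** With X1 ~ Bin(11, p) and X2 ~ Bin(24, p):

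- P(stop at stage 1) = P(X1 ≤ 1) = 0.697 at p = 0.1 and 0.113 at p = 0.3. Section 4.2 states 0.70 and 0.11.
- P(success) = Σ over x = 2 to 11 of P(X1 = x) · P(X2 ≥ 7 − x) = 0.0422 at p = 0.1 and 0.851 at p = 0.3.

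A search for the optimal design at 0.05 and 0.15 returns 1/11 and 6/35. The design reproduces as stated, with the cut-off of 6 applied to the total over both stages.

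**2. How often the rules can conflict: ceiling.** P(X1 ≥ 2) minus P(X1 ≥ 2 and total ≥ 7 of 35):

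| True response rate | Pass stage 1 | 7 or more of 35 | 6 or fewer of 35 after stage 1 |
|---|---|---|---|
| 10% | 0.3026 | 0.0422 | 0.2604 |
| 20% | 0.6779 | 0.4696 | 0.2082 |
| 30% | 0.8870 | 0.8510 | 0.0360 |

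**3. How often a drug group is short.** This needs the drug mix, which the documents do not give. Below is the exact multinomial probability that at least one of the four drugs has fewer than 5 patients. It is shown for 35 patients and for 44, because the trigger does not say whether evaluable or enrolled patients are counted. The second to fourth rows assume that enrolled patients follow the Section 1.1 frequencies, although those describe melanocytic neoplasms including melanomas. The scale is entrectinib 17 + 16 = 33, ceritinib 10, regorafenib 5 + 3 = 8, and an assumed MET figure for capmatinib.

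| Assumed mix | 35 patients | 44 patients |
|---|---|---|
| Equal shares | 0.162 | 0.029 |
| Section 1.1, MET = 5 | 0.936 | 0.772 |
| Section 1.1, MET = 3 | 0.986 | 0.937 |
| Section 1.1, MET = 1 | >0.999 | 0.999 |

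If response is independent of drug, the conflict probability is the product of steps 2 and 3. At a true rate of 10%, equal shares give 0.162 × 0.2604 = 0.042 (35 patients) or 0.029 × 0.2604 = 0.008 (44 patients). MET = 5 gives 0.936 × 0.2604 = 0.244 or 0.772 × 0.2604 = 0.201.

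**4. Type I error if the decision is made at 35.** Success requires 7 or more responses in the first 35, so it is 0.0422. If termination is honoured and later patients are pooled, it is still 0.0422: only trials already at 7 or more continue, and added patients cannot lower the count.

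**5. Type I error if the stop is overridden, added patients are pooled and the cut-off of 6 is kept.** Replace Bin(24, p) by Bin(N − 11, p) at p = 0.1:

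| Evaluable patients N | Type I error |
|---|---|
| 35 | 0.042 |
| 36 | 0.047 |
| 37 | 0.052 |
| 40 | 0.068 |

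The row N = 40 is the cap after drop-out: 50 × 0.8 = 40. These figures assume that every trial passing stage 1 goes on to N.

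**The case against.** The best counter-argument is that the text already implies an order. A terminated trial cannot enrol, so the extension concerns only trials with 7 or more responses. The abstract and Section 9 also fix the decision at 11 + 24 patients and a maximum of 35 evaluable, so carrying the cut-off of 6 to a larger pooled set would contradict them. On that reading type I error is 0.042.

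Much of this stands. A reader might infer that the five-per-drug rule inflates the type I error. The documents do not support that. Inflation needs three departures together, none is stated, and the abstract and Section 9 argue against them. Nor can a firm lower limit be put on how often the rules conflict. Any such figure rests on an assumed drug mix, and equal shares bring it down to a few percent or less.

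The sequential reading does not remove the gap, however. Accrual to 35 is complete when the final rule applies, so termination there can also be read as a verdict of not promising. The minimum of five per drug serves a purpose that does not depend on the pooled result, and a sponsor could legitimately want those small groups completed for description and safety. Even under the sequential reading, the plan does not say whether patients added after a positive result enter the pooled analysis.

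**Conclusion.** The point holds as a conflict between stated rules and stated sizes, and it should be fixed. Section 4.2 gives two incompatible instructions for a trial with 6 or fewer responses in 35 and a short drug group, and its cap of 50 enrolled is missing from Section 9 and the abstract.

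The situation can arise in at most 26.0%, 20.8% and 3.6% of trials at true response rates of 10%, 20% and 30%. Those ceilings are exact for the stated design. The actual frequency depends on the drug mix. A short group occurs in about 16% of trials (35 patients) or 3% (44 patients) with equal shares, and in over 90% at 35 patients if shares follow Section 1.1 and MET is assumed to be 5 or less on that scale.

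The design itself is sound: type I error 0.042 and power 0.851 when decided at 35. The 0.052 and 0.068 show what an unwritten choice could cost. They are not properties of the plan.

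**What to change.** In Sections 4.2 and 9, state that the composite go/no-go decision is made once, on the first 35 evaluable patients (11 + 24), and requires at least 7 responses in total across both stages. This also settles the Section 9 wording that applies the cut-off of 6 to the second stage.

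State that patients enrolled under the five-per-drug rule do not enter that test. They may be included in per-drug, safety and descriptive summaries, labelled as such. They need not be barred from pooled descriptive estimates to protect the test.

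The sponsor should reconcile the two paragraphs of Section 4.2 by saying whether five-per-drug enrolment still applies after a negative composite result. Either answer leaves the type I error at 0.042 once the test is fixed on the first 35. The cap of 50 enrolled should appear in Section 9 and the abstract.

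The cost is a few sentences and no extra patients. Type I error and power stay at 0.042 and 0.851. The only downside is that added patients do not contribute to the primary test.

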5.3 Packaging and Labeling of Study Drugs

Drugs will be packaged and labeled per UCSF institutional standards, adhering to applicable local and federal laws.

6 Treatment Plan

Patients will be treated with an appropriate kinase inhibitor as outlined in Table 1. Cycle length is defined for this study as 4 weeks. Patients will be restaged every 2 cycles (8 weeks), and best objective response will be confirmed using RECIST v1.1 with measurements at a minimum of 4 weeks after the response-defining determination. Dose reductions and dose interruptions for management of toxicity will be specified in the sections below.

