8.1 Evaluation of Efficacy (or Activity)

Evaluation of efficacy to be assessed by ORR and CBR, using RECIST v1.1 criteria.

Response and progression in this study will be evaluated using the new international criteria proposed by the Response Evaluation Criteria in Solid Tumors ([RECIST](#)) Committee²⁸. Changes in only the largest diameter (unidimensional measurement) of the tumor lesions are used in the RECIST v1.1 criteria. Local review of response or progression will be performed at each site. Data for each patient with a response will be reviewed at UCSF.

Definitions

Evaluable for toxicity

All patients will be evaluable for toxicity from the time of their first treatment with the study drug.

Evaluable for objective response

Only those patients who have measurable disease present at baseline, have received at least one cycle of therapy (with at least 90% of intended dosing administered during cycle 1), and have had their disease re-evaluated will be considered evaluable for response. These patients will have their response classified according to the definitions stated below. (Note: Patients who exhibit objective disease progression prior to the end of Cycle 1 will also be considered evaluable.)

Disease Parameters

Measurable disease

Measurable disease is defined as the presence of at least one measurable lesion by radiographic assessment or by clinical examination (e.g., skin lesion). If the measurable disease is restricted to a solitary lesion, its neoplastic nature should be confirmed by cytology/histology. Positive bone scans and radiographic studies of bone involved with tumor are not considered to be measurable disease.

All tumor measurements will be recorded in millimeters or decimal fractions of centimeters. Previously irradiated lesions are considered non-measurable except in cases of documented progression of the lesion since the completion of radiation therapy.

Target lesions

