SD	Non-PD	No	SD	documented at least once > 4 weeks from baseline
PD Any Any	Any PD* Any	Yes or No Yes or No Yes	PD PD PD	no prior SD, PR or CR

* In exceptional circumstances, unequivocal progression in non-target lesions may be accepted as disease progression

Patients with a global deterioration of health status requiring discontinuation of treatment without objective evidence of disease progression at that time should be reported as “symptomatic deterioration”. Every effort should be made to document the objective progression even after discontinuation of treatment.

The best overall response for an early death, i.e., a patient who dies without documentation of disease progression and before it was time to conduct the first tumor reassessment, will be considered inevaluable or not assessed adequately. Response will also be considered inevaluable for any patient receiving treatment (regardless of how much was received) who did not have any follow-up assessment completed before initiation of alternative treatment.

In some circumstances it may be difficult to distinguish residual disease from normal tissue. When the evaluation of complete response depends upon this determination, it is recommended that the residual lesion be imaged by PET scan or be investigated by fine needle aspirate/biopsy before confirming the complete response status.

Duration of Response

Duration of overall response

The duration of overall response is measured from the time measurement criteria are met for CR or PR (whichever is first recorded) until the first date that recurrent or progressive disease is objectively documented (taking as reference for progressive disease the smallest measurements recorded since the treatment started).

The duration of overall CR is measured from the time measurement criteria are first met for CR until the first date that recurrent disease is objectively documented.

Duration of stable disease

Stable disease is measured from the start of the treatment until the criteria for progression are met, taking as reference the smallest measurements recorded since the treatment started.

Progression-Free Survival

Progression-free survival (PFS) is defined as the duration of time from start of treatment to time of progression.

Evaluation of Safety

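### The two-stage design is counted in evaluable patients, but sections 4.2, 8.1 and 9 define evaluable in conflicting ways and none is said to govern

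*Combined protocol and SAP*

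**What the plan says.** Sections 4.2 and 9 both size the trial at 35 evaluable patients, with 44 enrolled and treated to allow for 20% drop-out. Section 9 puts it this way: "In this scenario, the maximum trial size would be 35 evaluable patients". The stopping rules are 1 or fewer responses in the first 11 and 6 or fewer in 35. The stage 1 text speaks only of the initial 11 patients. That these are evaluable patients is inferred from 11 + 24 = 35.

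The definitions are:

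- **Section 4.2:** "Evaluable patients would be those with baseline staging, treatment for at least 8 weeks, and at least one post-baseline staging scan while on treatment".
- **Section 9:** baseline staging, "treatment for at least one cycle (with at least 90% of intended doses administered during cycle 1", and a scan while on treatment.
- **Section 8.1, Evaluable for objective response:** "Only those patients who have measurable disease present at baseline, have received at least one cycle of therapy" at the same 90% dosing level, and have been re-evaluated. A note adds: "Patients who exhibit objective disease progression prior to the end of Cycle 1 will also be considered evaluable".

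Under Evaluation of Best Overall Response, section 8.1.1.1 gives a response category to two further groups. A patient who dies without documented progression, "before it was time to conduct the first tumor reassessment, will be considered inevaluable or not assessed adequately". So is the response of any treated patient "who did not have any follow-up assessment completed before initiation of alternative treatment".

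On timing, section 6 says: "Patients will be restaged every 2 cycles (8 weeks), and best objective response will be confirmed using RECIST v1.1", with confirmation at least 4 weeks after the response is first seen. Section 7.1 allows visit procedures a 7-day window either way unless otherwise noted. Section 4.4 lists progression among the reasons that require treatment to stop. The set of patients with at least one dose is named only under Evaluation of Safety (sections 8 and 9.1). No denominator is stated for the primary ORR.

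**The concern.** The stop/continue decision and the primary ORR both need a denominator, and the protocol gives more than one. Sections 4.2 and 9 attach different rules to the same 35 patients and the same boundaries, so one set of data can meet the success criterion under one section and miss it under the other. If the choice is left open until responses are known, a single-arm result loses much of its credibility. The primary objective is estimation, so the denominator matters even apart from the test.

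The section 4.2 rule adds a problem of its own: it removes patients according to how early their treatment failed.

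**Working it through.** **Step 1. Reproduce the plan's design.** Inputs from section 4.2 and the abstract: rates 10% and 30%, stop if 1 or fewer of 11 respond, success if 7 or more of 35 respond in total, drop-out 20%. With X1 ~ Bin(11, p) and X2 ~ Bin(24, p):

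- P(stop at stage 1) = P(X1 ≤ 1) = 0.697 at p = 0.10 and 0.113 at p = 0.30. The plan states 0.70 and 0.11.
- pass(p) = Σ over x ≥ 2 of P(X1 = x) × P(X2 ≥ 7 − x) = 0.0422 at p = 0.10 and 0.8510 at p = 0.30.
- 35 / (1 − 0.20) = 43.75, rounded up to 44.

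The design reproduces. The difficulty is who is counted in it.

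**Step 2. Apply the three definitions to the same patients** (all with measurable disease at baseline).

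| Patient | 4.2 | 9 | 8.1 |
|---|---|---|---|
| Objective progression before the end of cycle 1, treatment stopped | No | No | Yes |
| Adequate cycle 1 dosing, progression on a scan after cycle 1 but before 8 weeks are complete, treatment stopped | No (read literally) | Yes | Yes |
| 8 weeks of treatment and an on-treatment scan, but under 90% of cycle 1 dosing | Yes | No | No |
| Early death or stopping with no scan | No | No | No |

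The second row can arise on schedule if the general window applies. Week 8 is day 56, and 56 − 7 = 49, so a first scan 49 to 55 days after start is in window. Progression on it ends treatment before 56 days.

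**Step 3. Direction.** First restaging is at week 8 and confirmation comes at least 4 weeks later. A patient who stopped before week 8 can hardly be a confirmed responder, so the 8-week requirement removes almost only non-responders. The 90% rule in 8.1 and 9 can remove either kind.

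**Step 4. Size (illustration).** Let p be the response rate among 4.2-evaluable patients. Let g be the share of patients whom 4.2 drops but another definition keeps as non-responders. The documents give no g; 5% and 10% are assumed. The 90% rule is not modelled. The wider set then has rate p(1 − g). It adds only non-responders, so in enrolment order its first 11 or 35 never hold more responders than those of the 4.2 set. Hence P(pass under 4.2, fail under the other) = pass(p) − pass(p(1 − g)).

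| p | g | p(1 − g) | Difference |
|---|---|---|---|
| 0.30 | 5% | 0.285 | 0.8510 − 0.8150 = 0.036 |
| 0.30 | 10% | 0.27 | 0.8510 − 0.7718 = 0.079 |
| 0.20 | 5% | 0.19 | 0.4696 − 0.4165 = 0.053 |
| 0.20 | 10% | 0.18 | 0.4696 − 0.3629 = 0.107 |

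Opposite stage 1 decisions at p = 0.30: 0.1344 − 0.1130 = 0.021 for g = 5% and 0.1590 − 0.1130 = 0.046 for g = 10%.

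**The case against.** - **Closer to two definitions than three.** Sections 8.1 and 9 share one cycle, 90% dosing and re-evaluation, and section 7.1.1 has measurable disease documented for everyone. This stands in part. Sections 8.1 and 9 still differ on cycle 1 progression and on whether the scan must be on treatment, and section 4.2 conflicts with both.
- **The in-window case depends on unseen text.** The 7-day window holds only unless otherwise noted, and the drug-specific calendars were not supplied. The 8 weeks may simply mean reaching first restaging. For regorafenib, planned dosing in cycle 2 ends at day 49, before the week off. This stands: the case is conditional. The first and third rows of the table do not need it.
- **Larger effects do not measure this conflict.** Setting g at the full 20% drop-out would treat every drop-out as an early progressor kept by 8.1 or 9. Patients who are never scanned fail those definitions too. This stands, so only 5% and 10% are shown.
- **The one-way result comes from leaving out the 90% rule.** This stands. If 10% of patients are under-dosed independently of response (assumed), then at p = 0.30 and g = 5% a simulation gives about 0.06 passing under 4.2 only and about 0.02 passing under the other only. Disagreement does not shrink, but it runs both ways.
- **Silence is not exclusion.** A reader might infer that the plan rejects an all-treated ORR, or that section 8.1.1.1 removes early deaths from the denominator. The text supports neither: no ORR denominator is given, and section 8.1.1.1 assigns a response category only.

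**Conclusion.** The point holds as a contradiction in a rule on which the primary result depends. The protocol as written does not determine which patients make up the 11 and the 35. This follows from the wording alone and needs no assumption about g.

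Section 4.2's exclusion of patients who stop before week 8 inflates ORR; for sections 8.1 and 9 the direction is not established. The size is illustrative: a probability of 0.036 to 0.079 at a 30% rate, or 0.053 to 0.107 at 20%, of passing under 4.2 and failing under another definition, for an assumed 5% to 10% of patients and without the dosing rule.

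A reader might go further and infer that type I error is inflated. If 10% were an all-treated rate and the 20% excluded never responded, the evaluable rate would be 0.10 / 0.80 = 0.125 and the error 0.109. The documents do not say which set the 10% refers to, nor that drop-outs never respond. If 10% is an evaluable-patient rate, or drop-out is unrelated to response, the error stays at 0.042. Type I inflation is therefore not part of this finding.

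**What to change.** Before the stage 1 decision:

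1. Put one identical definition of the primary response set in sections 4.2, 8.1 and 9, and say that it applies to both the 11- and 35-patient counts. State explicitly whether the 90% dosing condition is part of it.
2. In that definition, keep treated patients with early progression, early death or stopping for early failure, and count them as non-responders.
3. Leave the 1/11 and 6/35 boundaries as they are.
4. Report ORR in all treated patients alongside as a sensitivity analysis: at least one dose, and anyone without a confirmed CR or PR counted as a non-responder.

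This is a change of wording. It needs no extra patients and alters neither the scan schedule nor the treatment rules. The cost is that the reported ORR may be somewhat lower.

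Making the all-treated set primary is optional, because it can cost power. If 30% was meant as an evaluable-patient rate and the 20% drop-outs never respond, the all-treated rate is 0.30 × 0.80 = 0.24. Power then falls from 0.851 to 0.662, and the chance of stopping at stage 1 rises from 0.113 to 0.219.
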